In the adjuvant setting, sterilizing microscopic disease potentially persistent after radical surgery, particularly in high-risk patients, represents the rationale of adding WPRT to prostatic bed radiotherapy in pN0 patients. Goldner et al. evaluated the clinical impact of prostate only adjuvant RT in pN0 patients showing a 5-year biochemical relapse free survival of 100% and 58% in patients with a risk of nodal involvement <15% and >15%, respectively. These findings may be explained by a microscopic involvement of pelvic structures (lymph nodes, bone) other than prostate bed. However, the role of adjuvant post-surgical WPRT need to be validated by large prospective studies, not actually ongoing to our knowledge. [37, 38, 39, 40]. Moreover, no clear-cut guidelines are available about the usefulness of adding ADT to adjuvant RT in the different subsets of pN0 patients.

On the other hand, nodal involvement (pN1) is a strong negative prognostic factor and adjuvant RT in these patients may be useful to optimize loco-regional control deferring first or second line systemic therapies [41]. Actually, the standard adjuvant treatment for pN1 PCa patients is represented by long term ADT, but the association with WPRT might significantly increase survival outcomes [42]. A recent analysis conducted by SEER on “pN1 M0” PCa patients treated with adjuvant WPRT seems to confirm the benefit obtained by the association of WPRT with ADT, demonstrating a survival advantage for intermediate risk patients [43].

Conclusions, rationale and summary of the study

In conclusion, open questions about ENI for prostate cancer still remain:

1. In the exclusive radiotherapy scenario, does ENI produce an overall or biochemical relapse free survival advantage over prostate only radiotherapy for intermediate/high/very high risk cases?
2. If ADT is added to prostate only radiotherapy, in intermediate/high/very high risk cases, ENI is any longer needed?

3. Is ENI, associated or not to ADT, linked with an OS or bRFS survival advantage in patients submitted to adjuvant postsurgical prostate radiotherapy?
4. Additional toxicity due to the larger volumes treated might be reduced by more sophisticated radiotherapy techniques when ENI is added to prostate?
5. How many Radiation Oncology centers use ENI to treat patients with intermediate/high/very high-risk prostate cancer, with or without ADT?

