We propose a no-profit, multicenter observational study to collect data of consecutive patients treated with ENI both in the exclusive radical radiotherapy scenario and in the adjuvant postsurgical setting. Cases treated both with and without associated ADT will be recruited to evaluate Overall survival (OS) (that will be the main endpoint), Cause-specific (CSS) and Biochemical Relapse Free survival (bRFS), toxicity and Quality of Life (QoL) (the secondary endpoints).

Aims of the study

Clinical features and outcomes will be assessed as better detailed in the following lines:

1. To define the diffusion of the practice of treating pelvic lymph-nodes in patients affected by intermediate/high/very high risk non-metastatic prostate cancer (PCa) among Italian Radiation Oncology Centres, submitted to radical or post-operative radiotherapy;
2. To define the diffusion of the different radiotherapy techniques used to treat pelvic nodes and the other features of the radiation treatment;
3. To register prospectively biochemical and clinical failure, prostate cancer deaths and deaths for any cause in the population studied;
4. To register prospectively the toxicity due to radiotherapy and androgen deprivation therapy in patients treated with pelvic nodes radiotherapy;
5. To compare clinical outcomes and toxicities observed in the different clinical and therapeutic subgroups with the corresponding historical data relative to PCa patients treated with radiotherapy with or without elective pelvic nodal irradiation, already available in the existing AIRO (Italian Society of Radiation Oncology) databases;

6. To exploit the collected data to define the need and the features of a prospective randomized trial evaluating the efficacy of elective pelvic nodal irradiation in patients with intermediate/high/very high risk non-metastatic prostate cancer.
7. The data obtained from the present observational study will be helpful for designing a subsequent randomized controlled trial.

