Centers involved will identify all the eligible cases with biopsy proven prostate adenocarcinoma. Patients who are candidate to get involved in the study will be contacted by the physician in charge of the study for each Center. **Every** prostate cancer patient consecutively evaluated at the recruiting Centers and planned to receive radical exclusive or post-operative radiotherapy will be registered; this registration includes demographic and staging results data; only intermediate, high, very high patients will have, however, treatment and follow up CRF compiled (both treated with or without ENI; +/- ADT).

Eligible patients will then receive all the information necessary to formulate their adhesion to the study and finally the physician will fill in the “Pretreatment” Case Report Form (CRF) that will include:

- Demographic Information (date of birth, study title, civil state, working information);
- Another person (relatives, friends,...) as a contact to minimize follow up loss;
- Anamnestic data (height, weight, smoking habit, comorbidities, Cumulative Illness Rating Scale [44], Attachment 1);
- Initial diagnosis (date; PSA at diagnosis);
- Risk factors;
- Staging (clinical TNM, date of biopsy, Gleason score, total number of samples, number of positive samples);
- Quality of life and symptoms caused by prostate cancer (using Italian UCLA Prostate Cancer Index) [45, 46];
- General quality of life (SF-12 Standard V1) [47].

The choice of the treatment will be done based on commonly used international guidelines and on the specific internal protocol of each participating Center.

Since this study is observational, involved patients will be treated following *good clinical practice* and institutional policies procedures.

Clinical outcomes, (such as overall survival and biochemical relapse free survival) and variables, demographic features, dosimetric analysis and acute/late toxicities of both RT and ADT will be reported.

Phase 3: Follow-up (1, 3, 6, 12, 18, 24, 30, 36 months)

After the end of the radiotherapy treatment patients will be evaluated 1, 3, 6, 12, 18, 24, 30 and 36 months since the last session.

Every patient will be contacted by the physicians to fill a CRF that will include:

- Vital state (mortality, date and causes of death) or loss to follow up;
- Last PSA value;

- Other treatments (drugs);

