In order to describe the data, mean and standard deviation will be used for normally distributed continuous variables, median and ranges for non-normally distributed continuous variables, proportions and percentages for categorical variables. Associations between two categorical variables will be assessed through the Pearson's chi-squared test or Fisher test, when appropriate. Differences between two-sample central tendencies will be assessed with a two independent sample t-test or Mann-Whitney U test or Wilcoxon, depending on distribution of the continuous variable.

Analysis of variance and covariance and regression models will be used for evaluating the associations of some variables with survival taking account of possible confounders.

In order to compare groups in terms of survival end-points, Kaplan-Meier curves will be estimated and log-rank tests will be performed.

Periodical analyses are planned in order to check the quality of entered data.

The analyses will be performed by using STATA 13 (StataCorp. 2013. Stata Statistical Software: Release 13. College Station, TX: StataCorp LP) or SPSS Statistical Software.

Ethical committee

After the final approval by the AIRO-PCSG, the Protocol will be submitted to the Ethical Committee (EC) of the Study Coordinating Centre; when it will be approved, the single participating Centres will consequently apply for approval of their EC. According to the judgment of the PI and of the Study Coordinator, the first patient will be enrolled when a sufficient number of Centres will have obtained EC approval. This will be the starting date for the study.

The present study will be performed in accordance with the present protocol, with the principles of Good Clinical Practice in the respect of the ICH GCP guidelines and the ethical principles contained in the Helsinki declaration.

Publication rules

Interim and final results of the study will be published under the final responsibility of the PI and of the Study Coordinator.

The following publication rules will be enforced:

1. The participating Centers should approve the paper;
2. Only Centers contributing to more than 5% of the cases collected will have a person quoted as Author of the paper; however, every Center contributing to the common database, as well as the people working to realize the Study, will be publicly quoted and their contribution acknowledged in the paper;
3. Authorship is granted in proportion to:
 - a. the cases contributed to the database;

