ATTACHMENT 3 – 3, 6, 9, 12, 18, 24, 36 MONTHS FOLLOW UP

	
1 He does not adhere anymore for health reasons, specify _____
 
2 He is not interested anymore to take part in the study
 
3 He is not traceable

Does the patient still undergo Hormonal Therapy?	
1. Yes
 
If yes: (FILL IN POINT 4 BELOW)
 
0 No
 
If no: Date of ending hormonal therapy  / /  day month year

Has he developed new comorbidities? (It is possible to fill in more than one option)	
0 . No
 
1 . Yes
 
If yes:
 
 1 Cardiac (specify _____) 2 Vascular (including hypertension) 3 Pulmonary (specify _____) 4 Eye, ear, nose, throat, larynx 5 Gastro-intestinal (specify _____) 6 Hepatic (liver only) 7 Renal (kidneys only) 8 Musculo-skeletal (specify _____) 9 Intertegumentary (skin) 10 Neurological (specify _____) 11 Endocrine-metabolic (specify _____) 12 Cognitive-psychiatric, behaviour 13 Genito-urinary (ureter-genitals) (specify _____) 14 Other malignancies (including Haematopoietic malignancies)

	15 Other, specify _____	
Has he undergone further treatments for prostate cancer, subsequent to those reported in Attachment 1 (1-month follow up)?	0 No	
	1 Yes	
	If yes:	
	1	Surgery
	2	External Beam Radiation Therapy
	3	Brachytherapy
	4	Radiometabolic Therapy
	5	Hormonal Therapy
	6	Focal Therapy
7	Chemotherapy	
8	Others, specify _____	

If he has undergone further treatments, specify:

Date of starting the new treatment |__|/|__|/|__|_|_|

day month year

PSA before starting the new treatment |__|_|_|_|. |__|_|_| ng/mL

 External Beam Radiotherapy	
Aim of Radiotherapy	1 Palliative
	2 Other, specify_____
Modality	1 IGRT
	2 Non IGRT
Technique	1 3D-CRT

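### ANOVA and ANCOVA are named for confounder-adjusted survival associations, no censored-data regression is named, and the log-rank comparison of groups is unadjusted

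*Combined protocol and SAP*

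**What the plan says.** Two consecutive sentences under Statistical Analyses, worded identically in the synopsis, cover the survival end-points. The first deals with adjustment: "Analysis of variance and covariance and regression models will be used for evaluating the associations of some variables with survival taking account of possible confounders". The second deals with group comparison: "In order to compare groups in terms of survival end-points, Kaplan-Meier curves will be estimated and log-rank tests will be performed".

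Neither sentence lists the variables or the confounders, names a regression for censored data, or mentions a stratified log-rank test.

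Three other parts of the plan bear on this:

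- **Allocation.** Under Phase 2: "The choice of the treatment will be done based on commonly used international guidelines and on the specific internal protocol of each participating Center".
- **Use of the results.** Question 1 in the rationale asks: "does ENI produce an overall or biochemical relapse free survival advantage over prostate only radiotherapy for intermediate/high/very high risk cases". Aim 6 is: "To exploit the collected data to define the need and the features of a prospective randomized trial".
- **Loss to follow-up.** The Phase 3 form records "Vital state (mortality, date and causes of death) or loss to follow up", and Attachment 3 offers the option "He is not traceable". As a safeguard, the pre-treatment form takes a second person "as a contact to minimize follow up loss".

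**The concern.** ANOVA and ANCOVA have no means of handling censoring. Fitted to observed survival time, they treat a patient who was alive when last seen as if he had died that day. A difference between groups in length of observation then looks like a difference in survival, or hides one.

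The log-rank test handles censoring but, as written, adjusts for nothing. If clinicians give ENI more often to higher-risk men, a crude comparison of ENI with prostate-only radiotherapy partly measures risk group.

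An analyst could fit ANCOVA to survival time, or report a crude log-rank result for ENI, and in either case be following the plan. Either result could enter the decision on whether and how to run a randomised trial.

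**Working it through.** **Inputs from the plan:** N = 400; 5-year OS 0.80; 2 years of accrual; 3 years of follow-up per patient (Study Duration; Accrual and timeline), or at least 3 years (Sample size).

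**Assumptions:** constant hazard; half the patients receive ENI; half are high-risk; hazard ratio (HR) 2 for high v intermediate risk; no true ENI effect. Loss rates and ENI shares are as stated at each step.

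**1. The plan's own figure.** 0.8 ± 1.96 × √(0.8 × 0.2/400) = 0.761 to 0.839. This reproduces the stated 0.76–0.84. It concerns one cohort and does not depend on the methods at issue here.

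**2. Deaths and censoring.**
- Hazard L = −ln(0.8)/5 = 0.0446 per year.
- Exactly 3 years: 0.8^(3/5) = 0.875 still alive, so deaths = 400 × 0.125 = 50.1 and about 87% of times are censored.
- Follow-up to a common closing date, uniform over 3–5 years (one reading of at least 3 years): about 65 deaths, 84% censored.

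**3. ANCOVA on observed time, 3-year follow-up.** Simulation with 4,000 runs per scenario. Loss times are uniform over 0–3 years, and both models contain ENI and risk group.

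| Loss, no ENI v ENI | ANCOVA rejects | Mean ENI shift | Cox rejects |
|---|---|---|---|
| 0 v 0 | 5% | about 0 | 4–5% |
| 10% v 10% | 5% | about 0 | 5% |
| 5% v 7.5% | 7–8% | −0.4 month | 4–5% |
| 5% v 10% | 16–17% | −0.8 month | 4–5% |

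The shift can be checked by hand. Mean observed time to 3 years is R(L) = (1 − e^(−3L))/L = 2.808 years. For a lost patient it is (3 − 2.808)/(3L) = 1.435 years. An extra 2.5% lost moves the mean by 0.025 × (2.808 − 1.435) × 12 = 0.41 month, and an extra 5% by 0.82 month. Solving R(hL) = R(L) − shift gives h = 1.19 and 1.38. So 5 or 10 more lost patients among 200 on ENI have the same effect on this scale as a true HR of about 1.19 or 1.38 against ENI. If the loss fell on the other group, the shift would favour ENI.

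**4. ANCOVA with a common closing date.** If ENI use rises from 40% in accrual year 1 to 60% in year 2, ENI patients are observed for less time. ANCOVA on time rejects in about 36–38% of runs, with a mean shift of about −0.17 year. With a rise from 45% to 55% it rejects in about 13–14%. Cox stays near 5%.

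**5. Unadjusted log-rank.** Crude HR = (a × 2 + (1 − a))/((1 − a) × 2 + a), where a is the ENI share among high-risk men and 1 − a the share among intermediate-risk men. z = ln(HR) × √(deaths/4).
- 60/40%: HR = 1.6/1.4 = 1.14; with 50.1 deaths z = 0.47, rejection 8%.
- 70/30%: HR = 1.7/1.3 = 1.31; z = 0.95, rejection 16%.
- With 65 deaths: 8% and 19%.
- Risk-adjusted Cox: 4–5%.

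**6. Precision cost of adjustment.** The 95% CI is the HR divided and multiplied by exp(1.96 × √(4/deaths)/√(4a(1 − a))), for equal ENI groups. With 50 deaths the factor is 1.74 unadjusted and 1.83 with 70/30 imbalance. With 65 deaths it is 1.63 and 1.70.

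**The case against.** The strongest reply is that this is loose wording and not a chosen wrong method. The sentence also names regression models and commits to taking confounders into account, and the next sentence shows that the authors recognise censoring. That stands. A reader might infer that the plan commits to ANCOVA on survival time, or that it has no adjusted survival analysis. The text supports neither. What remains is that the only adjusted methods named specifically are unsuitable for censored times, and that the general term beside them does not say which regression will be used.

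Second, heavy censoring does no harm by itself. A reader might infer that 87% censoring inflates the error rate, but step 3 shows that ANCOVA keeps 5% when follow-up is equal. The documents do not say that loss will differ by ENI, and they take a step to limit loss. The loss rates and the drift in ENI use are assumptions.

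Third, nothing says that the log-rank groups are ENI v no ENI. The design is described as descriptive, and no aim states a within-cohort ENI test; aim 5 looks to historical data. That is fair, but question 1 asks for this contrast on OS and bRFS, and the log-rank is the only test offered for comparing groups.

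Fourth, a reader might infer that variation between centres alone biases the comparison. In a simulation with 16 centres of 25 patients, ENI 80% in half and 20% in half, and a centre HR of 1.5, the crude test rejects 13–14% only when the high-ENI centres are also the high-hazard centres. It rejects 5% when the two are unrelated. The documents do not indicate which applies, so this supports a sensitivity analysis only.

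**Conclusion.** The point holds as a fault of specification that should be corrected before analysis. ANOVA and ANCOVA do not suit a censored end-point, no method that does is named for adjustment, and the named group comparison is crude in a non-randomised cohort. The wording is certain; the harm is conditional. Under the stated assumptions, false rejection runs from the nominal 5% (equal follow-up, balanced risk) to about 16–17% with 5% v 10% loss or a 70/30 split of ENI by risk. It reaches about 36–38% with a common closing date and ENI use rising from 40% to 60%.

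A reader might infer that the primary survival estimate or the sample size is undermined. This point does not bear on either: the sample size rests on the precision of a single-cohort OS estimate. Only adjusted associations and comparisons between groups are at risk.

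**What to change.** In Statistical Analyses and in the synopsis, restrict ANOVA and ANCOVA to uncensored continuous outcomes such as QoL scores, and add:

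> Adjusted associations with OS, CSS (cause-specific hazard) and bRFS, including ENI v no ENI, will be estimated by Cox regression with covariates fixed in advance; unadjusted log-rank comparisons of treatment groups are descriptive.

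Two further suggestions are not part of the error:

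- **A short covariate list suited to about 50–65 deaths.** For example ENI, risk group (intermediate v high/very high), age, CIRS total and ADT, stratified by radical v adjuvant setting. That is five terms, or about 10–13 deaths per term.
- **A centre-stratified repeat of the model as a sensitivity analysis.**

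The cost is a change of wording in two places and some analyst time. Attachment 1 already collects date of birth, CIRS, PSA, TNM, Gleason score and the aim of radiotherapy; Attachment 2 collects target volumes and hormonal therapy. No patients or visits are added. The downside is the modest loss of precision in step 6. Intervals are wider still if the ENI groups are unequal: with 50 deaths and 20% on ENI, the unadjusted factor is already 2.00.

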Rationale	
Open questions are still needed to be answered:
 
 - In the exclusive radiotherapy scenario, does ENI produce an overall or biochemical relapse free survival advantage over prostate only radiotherapy for intermediate/high/very high-risk cases? - If ADT is added to prostate only radiotherapy, in intermediate/high/very high-risk cases, ENI is any longer needed?

	
 - Is ENI, associated or not to ADT, linked with an OS or bRFS survival advantage in patients submitted to adjuvant postsurgical prostate radiotherapy? - Additional toxicity due to the larger volumes treated might be reduced by more sophisticated radiotherapy techniques when ENI is added to prostate? - How many Radiation Oncology centers use ENI to treat patients with intermediate/high/very high-risk prostate cancer, with or without ADT? - The data obtained from the present observational study will be helpful for designing a subsequent randomized controlled trial.
End-points	
Primary:
 
 - Overall survival; 
Secondary:
 
 - Cause-specific (CSS) and Biochemical Relapse Free survival (bRFS); - acute and late toxicity evaluation (rectal, bladder, bowel toxicity, according to CTCAE v.4 scale); - Quality of Life deterioration (according to the UCLA-PCI scale).
Study design	
This is a prospective, multicenter, observational cohort study aimed to describe the advantage/disadvantage of different treatments of patients with intermediate/high/very high risk prostate cancer, through a web-based database.
 
The study will include all consecutive patients affected by intermediate, high or very high-risk prostate cancer that fit to the inclusion criteria and who are evaluated at each Centre involved in the study. Patients may have already undergone or not to radical prostatectomy and/or pelvic lymphadenectomy.
 
Phase 1: Establishment of the network of Centers involved in the study Phase 2: Activation and recruitment of eligible cases Phase 3: Follow-up (1,3,6,12/18,24/30/36 months)

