Statistical considerations	
Sample size
 
From previous experiences of the AIRO Prostate Cancer Study Group (AIRO PCSG), at least 15-20 Radiotherapy Centers from different regions of the country will be able to participate to the study. It is conceivable an accrual of at least 400-500 patients within 2 years and a further follow up of at least 3 years for each patient. For intermediate and high risk patients, an overall survival at 5 years of 0.8 has been previously reported (RTOG 94-13). According to the primary end-point of the study, a sample size of 400 patients will allow to estimate a 5-year survival of 0.8 with 95% confidence interval of 0.76-0.84.
 
Statistical Analyses
 
In order to describe the data, mean and standard deviation will be used for normally distributed continuous variables, median and ranges for non-normally distributed continuous variables, proportions and percentages for

	
categorical variables. Associations between two categorical variables will be assessed through the Pearson's chi-squared test or Fisher test, when appropriate. Differences between two-sample central tendencies will be assessed with a two independent sample t-test or Mann-Whitney U test or Wilcoxon, depending on distribution of the continuous variable.
 
Analysis of variance and covariance and regression models will be used for evaluating the associations of some variables with survival taking account of possible confounders.
 
In order to compare groups in terms of survival end-points, Kaplan-Meier curves will be estimated and log-rank tests will be performed.
 
Periodical analyses are planned in order to check the quality of entered data. The analyses will be performed by using STATA 13 (StataCorp. 2013. Stata Statistical Software: Release 13. College Station, TX: StataCorp LP) or SPSS Statistical Software.

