In summary, the study aims at the definition of survival, toxicity and QoL data in a representative sample of intermediate, high and very high risk prostate cancer patients consecutively recruited in Italian Radiation Oncology Centres over two years. Parameters considered will be OS, CSS and bRFS, toxicity (rectal, bladder, bowel toxicity, according to CTCAE v.4 scale) and QoL (according to the SF-12 scale and UCLA-PCI scale). Primary end point will be OS. Secondary endpoints will be CSS, bRFS, gastrointestinal and genitourinary toxicity, QoL deterioration.

Study Design

This is a prospective, multicenter, observational cohort study aimed to describe the advantage/disadvantage of different treatments of patients with intermediate/high/very high risk prostate cancer, through a web-based database.

Study Duration

The recruitment period, taking into account the needed sample size (*v.infra*) will be of two years, followed by three-year follow up period for each patient, with an accrual of at least 400-500 patients.

Population, Procedures

The study will include all consecutive patients affected by intermediate, high or very high-risk prostate cancer that fit the inclusion criteria and who are evaluated at each Centre involved in the study. Patients may have already undergone or not to radical prostatectomy and/or pelvic lymphadenectomy.

Inclusion criteria

- Men older than or aged 18 years;
- Histologically confirmed intermediate, high or very high risk prostate cancer patients (NCCN classification: Intermediate Risk T2b and T2c or Gleason Score 7 or PSA value between 10 and 20 ng/mL; High risk: T3a or Gleason score 8-10 or PSA > 20 ng/ml; Very high risk: T3b-T4 or patients with multiple adverse risk factors reported in the high risk category that may be shifted in the very high risk group
- Patients eligible for -and actually submitted to- radical radiotherapy treatment (+/- androgen deprivation) or adjuvant radiotherapy treatment after surgery (radical prostatectomy +/- pelvic lymphadenectomy);
- No other synchronous or previous malignant tumor other than skin basal cell carcinoma;
- Patients able to understand and sign the appropriate informed consent;
- Patients able to fill the QoL questionnaire;

Exclusion criteria

- Patients aged less than 18;

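### Quality-of-life deterioration is a secondary endpoint, but the listed tests that would fit a group comparison of it are unadjusted, and the confounder-adjusted models are tied to survival

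*Combined protocol and SAP*

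**What the plan says.** The synopsis (End-points) and the summary that closes Aims of the study both make QoL a secondary endpoint; the latter reads "Secondary endpoints will be CSS, bRFS, gastrointestinal and genitourinary toxicity, QoL deterioration". The questionnaires are completed before treatment (Phase 2, pretreatment CRF) and at the follow-up visits.

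Statistical Analyses, worded alike in the synopsis and the body, does not mention QoL. For a continuous variable it says "Differences between two-sample central tendencies will be assessed with a two independent sample t-test or Mann-Whitney U test or Wilcoxon". Two categorical variables are compared by chi-squared or Fisher tests. Confounders appear once: "Analysis of variance and covariance and regression models will be used for evaluating the associations of some variables with survival taking account of possible confounders". Kaplan-Meier curves and log-rank tests are for survival endpoints.

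The study is "aimed to describe the advantage/disadvantage of different treatments of patients with intermediate/high/very high risk prostate cancer" (Study Design). Under Phase 2, treatment is chosen from international guidelines and each centre's own protocol. Both radical and post-prostatectomy patients are eligible.

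**The concern.** The plan recognises that survival comparisons in this cohort need adjustment. QoL is measured in the same non-randomised patients, but the text makes no such provision for it.

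The UCLA-PCI asks about leakage, pads and erections, all of which surgery can affect before radiotherapy starts. Pretreatment scores may therefore differ between settings. If the use of elective nodal irradiation (ENI) also differs by setting or centre, an unadjusted comparison of ENI with no ENI mixes these differences with any treatment effect. It also ignores a baseline score that would sharpen the estimate. A result reached this way could mislead the planning of the randomised trial that the study is meant to inform.

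**Working it through.** **1. Text check.** Every method in Statistical Analyses, with the outcome it is tied to:

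| Method | Outcome named | Confounders |
|---|---|---|
| Means, medians, proportions | any variable | no |
| Chi-squared, Fisher | two categorical variables | no |
| t-test, Mann-Whitney, Wilcoxon | continuous variable, two samples | no |
| Analysis of variance/covariance, regression | survival | yes |
| Kaplan-Meier, log-rank | survival endpoints | no |

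Whether deterioration is read as a change score or as a yes/no event, the matching listed test is unadjusted.

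**2. The plan's own figure.** The only computed figure is for overall survival: 0.8 ± 1.96·√(0.8·0.2/400) = 0.8 ± 0.0392, or 0.761–0.839. This reproduces the stated 0.76–0.84. No QoL standard deviation, effect, group split or power is given, so all that follows is illustration.

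**3. Assumed inputs.** No treatment effect; two-sided 5%; complete questionnaires; equal groups of 200 (the planned 400) or 100 (one setting of 200, assumed); baseline/follow-up correlation r from 0.4 to 0.7; baseline gap d of 0.1 or 0.3 SD.

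**4. Gap that shrinks.** The expected follow-up difference is r·d. With SE = √(2/n) in SD units:
- change score: z = d(1−r) / [SE·√(2(1−r))]
- follow-up score: z = d·r / SE
- rejection rate = Φ(z−1.96) + Φ(−z−1.96)

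Example: for d = 0.3, r = 0.5, n = 200, SE = 0.1 and z = 0.15/0.1 = 1.5. The rate is Φ(−0.46) + Φ(−3.46) = 32.3%.

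| Per group | d (SD) | Change score, r = 0.4 → 0.7 | Follow-up score, r = 0.4 → 0.7 |
|---|---|---|---|
| 200 | 0.1 | 8.5% → 6.7% | 6.9% → 10.8% |
| 100 | 0.1 | 6.7% → 5.9% | 5.9% → 7.9% |
| 200 | 0.3 | 37.6% → 21.3% | 22.4% → 55.6% |
| 100 | 0.3 | 21.3% → 13.0% | 13.6% → 31.8% |

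**5. Gap that persists.** Simulated with setting split 65% v 35% between groups and a lasting 0.6 SD setting difference, a gap of (0.65 − 0.35)·0.6 = 0.18 SD. Change scores reject 4.8–5.6%. Baseline-only ANCOVA rejects about 12–19% with 200 per group and about 7–12% with 100. Baseline plus setting returns to 4.7–5.1%.

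**6. Precision.** Residual variance is 1−r² for ANCOVA, 2(1−r) for change and 1 for follow-up. ANCOVA cuts it by (1−r)/2 = 15–30% against change and r² = 16–49% against follow-up. With 100 per group and 80% power, the follow-up score detects (1.96+0.84)·√(2/100) = 0.40 SD. Multiplying by √(2(1−r)) gives 0.31–0.43 for change, and by √(1−r²) gives 0.28–0.36 for ANCOVA.

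**7. Centre.** Simulated with 15 centres of 27 or 20 of 20, half giving ENI to 90% of patients and half to 10%, r = 0.5, residual intraclass correlation 0.02–0.05, baseline-adjusted. Ignoring centre rejects 8–16% when centre effects are independent of ENI policy. Clustered standard errors with (centres − 1) degrees of freedom then reject about 5–6%. If centre effects correlate with ENI policy they reject about 8–16% (assumed correlation 0.3) and 16–30% (0.5). Fixed centre terms stay at about 4–7% throughout, with standard errors 1.3–1.6 times those of the clustered analysis (for example 0.146/0.095 and 0.144/0.111).

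**The case against.** The strongest reply is that no QoL comparison is planned. None of the listed aims compares QoL; the one comparative aim concerns clinical outcomes and toxicities against historical data. The questions posed separately by setting, such as "In the exclusive radiotherapy scenario, does ENI produce an overall or biochemical relapse free survival advantage over prostate only radiotherapy", concern survival and biochemical relapse. A reader might infer that the plan commits to an unadjusted QoL comparison. The documents do not say that, and a descriptive report would be consistent with the aims. What stands is that the design sentence speaks of weighing different treatments, so a comparison is a reasonable expectation, and only unadjusted tests are then on offer.

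Second, ANOVA and ANCOVA are methods for continuous outcomes and do not handle censored survival. The authors may have meant them for endpoints such as QoL. This is plausible, and a short correction would then close most of the gap, but the wording in both places names survival only.

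Third, change scores already use the baseline. That protects when a gap persists but not when it shrinks; baseline-only ANCOVA has the opposite weakness. Neither is safe alone.

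Fourth, because ENI may follow centre policy, a reader might infer that clustered standard errors should be the main analysis and fixed centre terms only a check. That does not follow. Clustering widens the standard error but does not remove bias when centre effects are related to policy. Treatment is chosen partly by centre protocol, so independence cannot be presumed.

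**Conclusion.** The gap holds as a matter of text: a named secondary endpoint has no stated analysis, every listed test that fits it is unadjusted, and the confounder provision is worded for survival. Adjusting for the baseline score and setting is a better method that the planned data already support.

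The size is unknown. A 0.1 SD gap that shrinks raises change-score rejection only to 5.9–8.5%; reaching 13–38% takes an assumed 0.3 SD; a persisting gap leaves it at 5%. A reader might take the larger figures as estimates of this study's error rate. They are not, since the gap, correlation, split and centre effects are all assumed. The precision gain does not depend on a gap existing, though its size depends on the assumed correlation. The primary endpoint is unaffected.

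**What to change.** In both Statistical Analyses sections, extend the confounder-adjusted models to QoL, or state that QoL will only be described. If groups are compared (ENI v no ENI):

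- Use a baseline-adjusted ANCOVA or a repeated-measures mixed model, with risk group, age and androgen deprivation as covariates.
- Stratify by or adjust for setting (radical/adjuvant). First reconcile the codes: Attachment 1 has definitive and adjuvant, while Attachment 2 adds salvage post-operative and other.
- Report unadjusted change scores as a sensitivity analysis.
- Account for centre in two ways and show both. Fixed centre terms protect against confounding by centre but have larger standard errors. A random effect, or clustered standard errors with (centres − 1) degrees of freedom, is more precise but valid only if centre effects are unrelated to ENI policy. Do not rank the second above the first because ENI follows centre policy.

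Cost: plan wording and a little more analysis work, with no extra patients or visits. Baseline scores, setting, staging, date of birth and hormonal-therapy category are already on the CRFs. Downsides: results depend on the modelled covariates, unmeasured confounding remains, and ANCOVA can be biased if a gap persists for a reason outside the model.
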